NON-INTERVENTIONAL (NI) STUDY PROTOCOL

Study information

Title	Assessment of 13-valent pneumococcal conjugate vaccine effectiveness among people with HIV in the United States
Protocol number	B1851217
Protocol version identifier	3.0
Date	06 December 2023
Active substance	
Medicinal product	Prevnar 13
Research question and objectives	
The primary objectives include:
 
1. Estimate vaccine effectiveness (VE) of PCV13 for invasive pneumococcal disease (IPD) among people living with HIV (PLWH) ≥ 18 years of age, overall and, if feasible, at 3, 5, and 7 years of follow-up2. Estimate VE of PCV13 for pneumococcal pneumonia among PLWH ≥ 18 years of age, overall and, if feasible, at 3, 5, and 7 years of follow-up3. Estimate VE of PCV13 for all-cause pneumonia among PLWH ≥ 18 years of age, overall and, if feasible, at 3, 5, and 7 years of follow-up 
The secondary objectives of this study are to estimate:
 
1. Estimate VE of PCV13 for pneumococcal pneumonia or pneumonia with unspecified causes among PLWH ≥ 18 years of age, overall and, if feasible, at 3, 5, and 7 years of follow-up2. Estimate VE of PCV13 for pneumonia with unspecified causes among PLWH ≥ 18 years of age, overall and, if feasible, at 3, 5, and 7 years of follow-up

Author	PPD [REDACTED], PhD, MPH Pfizer, Inc. PPD [REDACTED]
--------	--

This document contains confidential information belonging to Pfizer. Except as otherwise agreed to in writing, by accepting or reviewing this document, you agree to hold this information in confidence and not copy or disclose it to others (except where required by applicable law) or use it for unauthorized purposes. In the event of any actual or suspected breach of this obligation, Pfizer must be promptly notified.

2. LIST OF ABBREVIATIONS

Abbreviation	Definition
AE	Adverse event
ART	Antiretroviral therapy
CAP	Community-acquired pneumonia
CAPiTA	The Community-Acquired Pneumonia Immunization Trial in Adults
CI	Confidence interval
CIOMS	Council for International Organizations of Medical Sciences
CPT	Current procedural terminology®
CSF	Cerebrospinal fluid
EC	Ethics Committee
EMA	European Medicines Agency
ENCePP	European Network of Centres for Pharmacoepidemiology and Pharmacovigilance
FDA	Food and Drug Administration
GEP	Good Epidemiological Practice
GPP	Good Pharmacoepidemiology Practices
HCPCS	Healthcare Common Procedure Coding System
HIPAA	Health Insurance Portability and Accountability Act
HIV	Human immunodeficiency virus
HR	Hazard ratio
ICD-9-CM	International Classification of Diseases, Ninth Revision, Clinical Modification

Abbreviation	Definition
ICD-10-CM	International Classification of Diseases, Tenth Revision, Clinical Modification
ICD-9-PCS	International Classification of Diseases, Ninth Revision, Procedure Coding System
ICD-10-PCS	International Classification of Diseases, Tenth Revision, Procedure Coding System
IEA	International Epidemiological Association
IPD	Invasive pneumococcal disease
IRB	Institutional review board
ISPOR	International Society for Pharmacoeconomics and Outcomes Research
NDC	National Drug Code
PCV	Pneumococcal conjugate vaccine
PCV13	13-valent pneumococcal conjugate vaccine
PCV15	15-valent pneumococcal conjugate vaccine
PCV20	20-valent pneumococcal conjugate vaccine
PPSV23	23-valent pneumococcal polysaccharide vaccine
PLWH	People living with HIV
RZV	Recombinant zoster vaccine
SVI	Social Vulnerability Index
VE	Vaccine effectiveness
VT	Vaccine-type

4. ABSTRACT

Title	Assessment of PCV13 vaccine effectiveness among people with HIV
Rationale and background	
People living with HIV (PLWH) are at increased risk of pneumococcal infections. A recent meta-analysis shows that in the era of advanced antiretroviral therapy, the incidence of invasive pneumococcal disease (IPD) in PLWH is approximately 30 times higher when compared with the general population [1]. Even with timely and effective treatment, the case fatality rate of IPD is at least 8% in PLWH [2] and up to 25% of PLWH experience recurrent episodes of IPD in the subsequent 12 months [3].
 
International guidelines recommend pneumococcal vaccination for immunocompromised individuals [4] and previous research has shown that the pneumococcal conjugate vaccine (PCV) is safe and immunogenic in PLWH [5-8]. Studies have assessed the clinical efficacy/effectiveness of PCV in adults, but patients with immunocompromising conditions or treatments were either excluded from the studies, or vaccine effectiveness (VE) estimates were calculated overall and not specifically among PLWH or among people with other immunocompromising conditions [9, 10].
 
Given the lack of PCV13 VE data in immunocompromised adults, this study was designed to estimate PCV13 VE against pneumococcal disease in PLWH aged ≥ 18 years, overall and, if feasible, at 3, 5, and 7 years after vaccination.

Research objectives	
The primary objectives include:
 
1. Estimate vaccine effectiveness (VE) of PCV13 for invasive pneumococcal disease (IPD) among people living with HIV (PLWH) ≥ 18 years of age, overall and, if feasible, at 3, 5, and 7 years of follow-up2. Estimate VE of PCV13 for pneumococcal pneumonia among PLWH ≥ 18 years of age, overall and, if feasible, at 3, 5, and 7 years of follow-up3. Estimate VE of PCV13 for all-cause pneumonia among PLWH ≥ 18 years of age, overall and, if feasible, at 3, 5, and 7 years of follow-up 
The secondary objectives of this study are to:
 
1. Estimate VE of PCV13 for pneumococcal pneumonia or pneumonia with unspecified causes among PLWH ≥ 18 years of age, overall and, if feasible, at 3, 5, and 7 years of follow-up

	
2. Estimate VE of PCV13 for pneumonia with unspecified causes among PLWH ≥ 18 years of age, overall and, if feasible, at 3, 5, and 7 years of follow-up

Design	The VE study will be a retrospective cohort study using health care administrative claims and laboratory data.
Population	PLWH will be identified using administrative claims and include individuals with at least one inpatient International Classification of Diseases, Ninth Revision, Clinical Modification (ICD-9-CM) or International Classification of Diseases, Tenth Revision, Clinical Modification (ICD-10-CM) code related to HIV or at least 2 outpatient ICD-9-CM or ICD-10-CM codes related to HIV at least 30 days, but no more than 730 days apart, during January 1, 2014 and December 31, 2021. PLWH are required to have at least six months of continuous enrollment in one or more health plans and pharmacy benefits after their first HIV-related ICD-9-CM or ICD-10-CM. These six months of continuous enrollment will be considered the baseline period, during which baseline covariates including demographics, comorbidities, and preventative care will be measured. The end of the study will occur on the last date that administrative claims data will be available, September 30, 2022.
Data source	Health care administrative claims and laboratory data will be provided by Komodo Health. Komodo Health uses artificial intelligence and data analytics to combine and link patient-level information from more than 150 payers in the United States, including Medicare, Medicaid, and Commercial plans. Currently, Komodo Health has patient-level data on approximately 325 million individuals and these data include inpatient and outpatient claims, pharmacy dispensing claims, provider specialty claims, and mortality information.
Data analyses	
Cox proportional hazards models will be used to estimate the hazard ratio (HR) for each outcome comparing vaccinated PLWH with unvaccinated (no PCV13) PLWH. To explore potential changes in VE over time, HRs will also be generated during specific time periods (0-3, 3-5, 5-7 years) using piecewise Cox regression models, if there is adequate sample size. All models will be adjusted for time-fixed and time-varying covariates of interest using inverse probability of treatment weighting.
 
VE will be calculated as 1 minus the estimated HR for each outcome.

5. AMENDMENTS AND UPDATES

Version Identifier	Date	Amendment Type (substantial or administrative)	Protocol Section(s) Changed	Summary of Amendment(s)	Reason
2.0	02 August 2023	Substantial	9.1 Study Design	
 Individuals must now have at least one inpatient or at least two outpatient HIV-related ICD-9-CM and ICD-10-CM codes occurring at least 30 days but no more than 730 days apart Study follow-up will now begin 90 days after index date 	
 Limiting the time between outpatient HIV diagnosis codes decreases misclassification of HIV infection in administrative claims data Starting follow-up 90 days after index decreases the likelihood that outcome events occurred before and/or triggered an HIV diagnosis
			9.3 Variables	
 Added time-varying covariate for annual HIV viral load testing Added time-varying covariate for annual CD4 cell count testing Added time-varying covariate for respiratory virus season Added an alternate definition for outpatient candidiasis infection (ICD-9-CM or ICD-10-CM code and antifungal treatment within 7 days) Changed payor categories 	
 Minimize confounding due to different HIV care seeking patterns among PCV13 vaccinated and unvaccinated individuals Minimize confounding due to different HIV care seeking patterns among PCV13 vaccinated and unvaccinated individuals Minimize confounding due to increased risk for respiratory virus infections during fall and winter months Increase specificity of candidiasis infections within administrative claims Revised payor categories match actual payor categories in data provided by Komodo
			9.5 Study size	Added 'Total number of events' columns to Tables 2 and 3	Demonstrates that the study has sufficient statistical power for IPD and all-cause pneumonia outcomes
			9.7 Data analysis	Restricted stratified analysis by index year to first 3 years of follow-up	Due to possible waning of the VE and different lengths of follow-up by index year, VE stratification by year of HIV diagnosis will be restricted to the first 3 years of follow-up.
			Appendix	1. Added Appendix Table 9 for CD4 cell count laboratory CPT codes	Added Appendix Table 9, 10, and 13 as new variables are now included

				
 2. Added Appendix Table 10 for HIV viral load laboratory CPT codes 3. Added Appendix Table 13 for candidiasis antifungal NDCs 	
3.0	21 November 2023	Substantial	9.1 Study Design	
 1. Removed requirement for six months of continuous enrollment before members' first HIV-related ICD-9-CM or ICD-10-CM code 2. Study follow-up begins six months after the first HIV-related ICD-9-CM or ICD-10-CM code 	Analysis will include incident and prevalent HIV cases during 2014 - 2021, rather than only including incident cases during 2015-2021
			9.2.1 Inclusion criteria	
 1. Removed criterion for six months of continuous enrollment before first HIV-related ICD-9-CM or ICD-10-CM code 2. Require at least six months of continuous enrollment after the first HIV-related ICD-9-CM or ICD-10-CM code instead of 90 days. 	Analysis will include incident and prevalent HIV cases during 2014 - 2021, rather than only including incident cases during 2015-2021
			9.2.2 Exclusion criteria	Removed exclusion for individuals with evidence of ART therapy during baseline period	Analysis will include incident and prevalent HIV cases during 2014 - 2021, rather than only including incident cases during 2015-2021
			9.3 Variables	
 1. Added additional opportunistic infections to covariates measured during baseline and follow-up 2. Removed specific negative control exposure and negative control outcomes from table 	
 1. Control for potential confounding due to any opportunistic infection 2. Study team would like to explore additional negative control exposures and outcomes in analyses beyond Shingrix and candidiasis
			Appendix	Added additional ICD-9-CM and ICD-10-CM codes for opportunistic infections	Provided diagnosis codes to identify additional opportunistic infections

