7. RATIONALE AND BACKGROUND

Human immunodeficiency virus (HIV) infection leads to extensive defects in the immune system, including the progressive depletion and dysfunction of CD4⁺ T cells, perturbation of the B cell compartment with reduced resting memory B cells, and suboptimal humoral immune responses [11-14]. People living with HIV (PLWH) are at increased risk of pneumococcal infections. While antiretroviral therapy (ART) can restore the immune system and consequently lower the risk of pneumococcal infections [2, 15], the burden of pneumococcal infections persists in PLWH [16, 17]. A recent meta-analysis shows that in the era of advanced ART, the incidence rate of invasive pneumococcal disease (IPD) in PLWH is approximately 30 times higher when compared with the general population [1]. Even with timely and effective treatment, the case fatality rate of IPD is at least 8% in PLWH [2]. Up to 25% of PLWH experience recurrent episodes of IPD in the subsequent 12 months [3].

International guidelines recommend pneumococcal vaccination for immunocompromised individuals [4]. In the United States, one dose of 13-valent pneumococcal conjugate vaccine (PCV13) has been recommended to PLWH since 2012 [18]. Currently, the CDC recommends 20-valent pneumococcal conjugate vaccine (PCV20) alone or 15-valent pneumococcal conjugate vaccine (PCV15) followed by pneumococcal polysaccharide vaccine (PPSV23) for adults aged 19-64 years with certain underlying medical conditions, including HIV infection, and for all adults aged ≥ 65 years [19].

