9. RESEARCH METHODS

9.1. Study Design

The VE study will be a retrospective cohort study using health care administrative claims and laboratory data (Figure 1).

PLWH will be identified using administrative claims and include individuals with at least one inpatient International Classification of Diseases, Ninth Revision, Clinical Modification (ICD-9-CM) or International Classification of Diseases, Tenth Revision, Clinical Modification (ICD-10-CM) code related to HIV (Appendix Table 1) or at least 2 outpatient ICD-9-CM or ICD-10-CM codes related to HIV at least 30 days, but no more than 730 days apart, during January 1, 2014 and

PFIZER CONFIDENTIAL

December 31, 2021. PLWH are required to have at least six months of continuous enrollment in one or more health plans and pharmacy benefits after their first HIV-related ICD-9-CM or ICD-10-CM code. These six months of continuous enrollment will be considered the baseline period, during which baseline covariates including demographics, comorbidities, and preventative care will be measured. The baseline period was also selected to minimize the number of outcome events that existed prior to or triggered an HIV diagnosis.

The date following the last date of the baseline period will be defined as the index date. The end of the study will occur on the last date that administrative claims data will be available, September 30, 2022.

For PLWH who receive PCV13 after their index date, we will include the time between their index date and the 13 days after their PCV13 vaccination date as unvaccinated follow-up time. Any outcomes occurring during this time will be counted as events in the unvaccinated cohort. Follow-up that occurs 14 days or more after PCV13 vaccination will be defined as vaccinated follow-up time.

Unvaccinated (no PCV13) PLWH will be followed from index date until the earliest occurrence of the following: 13 days after PCV13 vaccination, death, end of health plan enrollment, or end of study period. Vaccinated PLWH will be followed from 14 days after their PCV13 vaccination, or index date if they were vaccinated during the baseline period, until the earliest occurrence of the following: death, end of health plan enrollment, or end of study period.

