9.3. Variables

Table 1. Variables, definitions, and measurement periods

Variable type	Variable	Definition	Measurement period
Exposure	PCV13 vaccination	Current procedural terminology® (CPT) codes and National Drug Codes (NDC) listed in Appendix Table 3	Follow-up
Primary outcomes	IPD	ICD-9-CM or ICD-10-CM codes listed in Appendix Table 4	Follow-up
	Pneumococcal pneumonia	ICD-9-CM or ICD-10-CM codes listed in Appendix Table 4	Follow-up
	All-cause pneumonia	ICD-9-CM or ICD-10-CM codes listed in Appendix Table 4	Follow-up
	Pneumococcal pneumonia or pneumonia with unspecified causes	ICD-9-CM or ICD-10-CM codes listed in Appendix Table 5	Follow-up
	Pneumonia with unspecified causes	ICD-9-CM or ICD-10-CM codes listed in Appendix Table 5	Follow-up
Covariates	Age	Calculated as [year individual meets HIV criteria] – [birth year] Categorized as 18-49, 50-64, 65-74, and ≥ 75 years	Baseline
	Sex	Male, Female, Other, Unknown	Baseline
	Social Vulnerability Index (SVI)	SVI characterizes resiliency of a community when faced by external pressures and stresses [25, 26]. SVI ranges from 0 to 100, where a value of 100 indicates the most vulnerable population. SVI will be estimated using zip code and will be categorized as low (lowest quartile), average (middle two quartiles) and high (highest quartile).	Baseline
	Payor	Medicaid/CHIP, Medicare, Commercial, Dually eligible, Other, Unknown	Baseline
	US region	Northeast, North Central, South, West, Unknown	Baseline

Variable type	Variable	Definition	Measurement period
	Index year	Calendar year of first HIV diagnosis code	Baseline
	Alcoholism	ICD-9-CM or ICD-10-CM codes listed in Annex Table 1.1	Baseline and follow-up
	Asplenia	CPT/Healthcare Common Procedure Coding System (HCPCS), ICD-10-Procedure Coding System (ICD-10-PCS), ICD-9-Procedure Coding System (ICD-9-PCS), ICD-9-CM, or ICD-10-CM codes listed in Annex Table 1.2	Baseline and follow-up
	Asthma	ICD-9-CM or ICD-10-CM codes listed in Annex Table 1.3	Baseline and follow-up
	Chronic heart disease	CPT/HCPCS, ICD-10-PCS, ICD-9-PCS, ICD-9-CM, or ICD-10-CM codes listed in Annex Table 1.4	Baseline and follow-up
	Chronic kidney disease and renal failure	CPT/HCPCS, ICD-10-PCS, ICD-9-PCS, ICD-9-CM, or ICD-10-CM codes listed in Annex Table 1.5	Baseline and follow-up
	Chronic liver disease	CPT/HCPCS, ICD-10-PCS, ICD-9-PCS, ICD-9-CM, or ICD-10-CM codes listed in Annex Table 1.6	Baseline and follow-up

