Several stratified analyses will be conducted. PPSV23 is recommended for PLWH and feasibility data provided by Komodo suggest that one in four PWLH who received PCV13 during 2014-2015 also received PPSV23 within two years. Rather than censor or exclude

individuals who receive PPSV23, we will calculate PCV13 VE among PWLH who have/have not received PPSV23 before and during the study period.

Feasibility assessments from Komodo indicate that approximately 25% of PWLH have at least one CD4 cell count or percentage laboratory result available. Therefore, we will calculate PCV13 VE among the subset of PWLH who have a CD4 cell count during the baseline period or follow-up, and potentially stratify by CD4 category using each patient's lowest value during the study.

Additional VE stratifications by ART adherence during follow-up, year of HIV diagnosis, and age will be assessed for feasibility as well, as these affect patients' immune status and immune reconstitution. Due to possible waning of the VE and different lengths of follow-up by index year, VE stratification by year of HIV diagnosis will be restricted to the first 3 years of follow-up.

A sensitivity analysis will also be conducted. In this analysis, causes of pneumonia that are characteristic of HIV, for example pneumonia due to cytomegalovirus, mycobacteria, and fungi, will be excluded from our definition of all-cause pneumonia.

Residual confounding of our VE estimates due to inadequate control for health care seeking behavior and immune status in our analyses will be explored. To do so, we will employ a negative control exposure and a negative control outcome. Potential negative control exposures include vaccinations that are recommended for PLWH but would not be expected to have any protective effect against the pneumonia outcomes of interest. If residual confounding does not exist, the negative control vaccine would not have an effect on the pneumonia outcomes. However, if the analysis demonstrates that the negative control vaccine protects against these outcomes, this suggests the presence of residual confounding.

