### 5.2.2. Exclusion Criteria

*Patients meeting the following criterion will not be included in the study:*

1. *Evidence of PCV13 vaccination before the first HIV-related ICD-9-CM or ICD-10-CM code*

All available data prior to first HIV-related ICD-9-CM or ICD-10-CM code will be used to assess evidence of PCV13 vaccination, however there is no minimum time requirement.

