### 5.3.2. Covariates

The list of demographic and clinical characteristics considered for descriptive reporting, subgroups and inclusion as covariates in models for generating the propensity scores are provided in Table 5.3. The Komodo Health database will be source of all variables.

Patients will be considered to have a comorbidity or hospitalization during baseline if there was evidence of a diagnosis at any time during the baseline period. Evidence of comorbidities or hospitalization during follow-up will be considered as new diagnoses. Once diagnosed, patients will be considered diagnosed for the remainder of their follow-up. ART adherence during baseline and follow-up will be updated every 6 months (180 days) based on the data collected in that previous timeframe. For baseline annual physical exam and annual influenza vaccine, patients will be considered adherent (coded as 'Yes') if there was evidence of these events at any time during the baseline period. During the follow-up, patients will be considered adherent up to 365 days after the last event date.

For annual CD4 and viral load laboratory tests during baseline and follow-up, patients will be coded as 'Yes' up to 365 days after the last event date. For respiratory virus season during follow-up, patients will be coded as 'Yes' if the observation time is in October, November, December, January, February, March or April.

The baseline period for the assessment of covariates is the six months prior to the index date, i.e., no data prior to six months will be included.

Covariates used at baseline only will be considered time-fixed confounders. Covariates additionally or only used during follow-up will be considered time-varying confounders.

Categories may be collapsed, or covariates may be excluded from the propensity scores if models fail to converge.

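### Newly diagnosed and established HIV are pooled with no covariate for HIV status at entry, so confounding by time since diagnosis and earlier ART is possible and only partly controlled

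*Protocol*

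**What the plan says.** The amendment table in Protocol 5 gives the reason for version 3.0: "Analysis will include incident and prevalent HIV cases during 2014 - 2021, rather than only including incident cases during 2015-2021". Although it stands in an amendment log, this describes the current design. Protocol 9.1 and 9.2.1 now require enrollment only after the first code ("PLWH are required to have at least six months of continuous enrollment in one or more health plans and pharmacy benefits after their first HIV-related" diagnosis code), and the only exclusion left in 9.2.2 is PCV13 before the first HIV code. The same amendment records: "Removed exclusion for individuals with evidence of ART therapy during baseline period".

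For covariates, SAP 5.3.2 restricts the baseline to the six months before the index date: "no data prior to six months will be included". For the PCV13 exclusion, SAP 5.2.2 does the opposite. It searches everything available before the first HIV code, "however there is no minimum time requirement".

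The variable called index year in Protocol Table 1, and year of HIV diagnosis in SAP Table 5.3, is "Calendar year of first HIV diagnosis code". Protocol 9.7 plans to stratify on it because it bears on immune status: "year of HIV diagnosis, and age will be assessed for feasibility as well".

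**The concern.** Earlier versions limited the range of disease stage by restriction. Version 3.0 lifts that restriction, so someone diagnosed last month and someone treated for years start on the same clock, and no planned variable tells them apart directly.

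On the protocol's own account, the difference matters for risk. Section 7 says "antiretroviral therapy (ART) can restore the immune system and consequently lower the risk of pneumococcal infections", and 9.7 calls immune status an important predictor of pneumonia while conceding that CD4 values will be missing for most people. In SAP Table 5.3, CD4 count is descriptive and a subgroup variable only, so it is not in the weights at all.

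Section 7 also says PCV13 is recommended to people with HIV, so uptake may plausibly vary with time since diagnosis; the documents do not show how. If uptake clusters near diagnosis, vaccinated time is enriched for higher-risk people and VE is pulled down. If new patients are vaccinated less, VE is pushed up. This is separate from the unrecorded PCV13 doses acknowledged in Protocol 9.9 and would remain if every dose were captured.

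**Working it through.** **1. What the covariates can see.**
- *Year of first code.* For a person with established HIV this is the year of entering the data, not the year of diagnosis. It is a covariate in SAP Table 5.3 but is missing from the time-fixed list in Protocol 9.7.
- *Baseline ART coverage.* It is read over the 180 days after the first code, with adherence defined as more than 80% of days covered. A new patient with 35 uncovered days has 145/180 = 80.6% and is adherent, like someone treated for years. With 36 uncovered days the figure is 144/180 = 80.0%, which is non-adherent. The variable separates late starters from established patients, but not early starters. The Missing category marks only people without ART information.
- *Opportunistic infections, hospitalization, baseline pneumonia, CD4 and viral-load testing.* These are correlates of disease stage, not measures of it.

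**2. The plan's own figures.** The vaccinated share reproduces: 56,000/175,000 = 32%. Protocol Table 3 gives 97-month intervals for all-cause pneumonia of 2% to 7% or 8% at VE 5%, and 13% to 17% or 12% to 18% at VE 15%: half-widths of about 2 to 3 points. The 36-month half-width is 4 points.

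**3. Illustrative size.** The documents give no newly diagnosed share, excess hazard or difference in uptake, so these are assumptions.
- Two groups, newly diagnosed (20%) and established, are followed in monthly steps for 97 months from index, with true HR 1.
- Base hazard is 5,000 per 100,000 per year (the plan has 5,487). Censoring is 7% per year (the plan has 4% or 10%).
- Established: 6% vaccinated at index and 6% per year after, which gives about 32% ever vaccinated overall in the doubled-uptake case.
- Newly diagnosed: hazard doubled for 24 months after index; uptake multiplied by u at index and for the same 24 months.
- Pooled HR = Σ(e1·n0/n) / Σ(e0·n1/n) over the monthly risk sets, where e is events, n is persons at risk, 1 is vaccinated and 0 is unvaccinated. VE = 1 - HR. No planned covariate is included.

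| Scenario (true VE 0) | Estimated VE |
|---|---|
| u = 2, 97 months | -3.0% |
| u = 0.5, 97 months | +1.8% |
| u = 2 during follow-up only, not at index | -1.4% |
| u = 2, both effects last 12 months | -1.3% |
| u = 2, both effects last 6 months | -0.6% |
| u = 2, excess hazard throughout follow-up | -8.3% |
| u = 0.5, excess hazard throughout follow-up | +4.9% |
| u = 2, first 36 months only | -7.8% |

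With higher uptake in the newly diagnosed, a share of 10% to 30%, a hazard of 1.5 to 3 times and an uptake of 1.5 to 3 times give -0.5% to -12.7%.

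**4. How far a proxy helps.** Suppose recent diagnosis doubles risk and makes up 10% of vaccinated and 20% of unvaccinated person-time. The bias factor is (1 + 0.10)/(1 + 0.20) = 0.917. Stratifying on an imperfect marker removes part of log(0.917): about 9% at sensitivity 0.8 and false-positive rate 0.4, 23% at 0.8 and 0.2, and 54% at 0.95 and 0.1. These accuracies are assumed. A perfect marker removes all of it.

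**The case against.** The strongest reply is that the plan is not without control.
- Version 3.0 itself lengthened the gap between first code and follow-up from 90 days to six months, so the time closest to diagnosis lies outside follow-up. It also widened the opportunistic-infection covariate.
- ART coverage is updated every 180 days, and ART is the route by which section 7 says risk falls. First-code year keeps 2014 as its own level, which plausibly absorbs many established cases.
- Residual confounding is acknowledged in Protocol 9.9, and 9.7 and SAP 5.8.8 suggest candidiasis as a negative control outcome for immune status, with possible bias correction. Stratification by ART adherence and first-code year will be assessed for feasibility.

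All of this stands. A reader might infer that nothing took the place of the old restriction, that no covariate carries any information on disease stage, or that every weighted VE is biased downward. The documents support none of these. Bias requires time since diagnosis to be related to both vaccination and outcome after the planned adjustment, and nothing in the documents shows that or gives its direction.

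The gap remains nonetheless. The proxies are partial. The negative controls can flag net bias but cannot attribute it to this mix, and correction is optional. Protocol 9.9 does not name the mix, and no newly-diagnosed-only analysis is planned.

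**Conclusion.** The point holds as a gap in confounder control, not as a demonstrated bias. Entry status and ART before the first code are unrecorded, and the SAP's covariate window prevents using earlier claims for them. Residual confounding is possible, with sign and size unknown.

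The central figures of about -3% and +2% rest on assumed inputs, on effects lasting two years after index and on no proxy control, so they do not measure the bias left after weighting. They are similar to the 2-to-3-point half-width planned for all-cause pneumonia at 97 months. Shorter-lived effects make them smaller; a lasting excess hazard, or the 0-3-year window, makes them larger. That is enough to justify an inexpensive covariate, but not enough to say that the VE estimates will be wrong.

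**What to change.** Add a time-fixed covariate, *HIV status at entry*, to SAP Table 5.3 and the list in Protocol 9.7:
1. Newly diagnosed: at least six months of medical and pharmacy enrollment before the first HIV code, with no ART dispensed in that time.
2. Established: ART dispensed before the first HIV code (this level takes precedence if both could apply).
3. Undetermined: everyone else.

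Include it in the weight numerators, the denominators and the marginal structural Cox models, as SAP 5.8.4 and 5.8.7 already do for time-fixed covariates, and exempt it from the six-month data rule in SAP 5.3.2. Name the mix of incident and prevalent cases as a limitation in Protocol 9.9.

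Report a newly-diagnosed-only sensitivity analysis for all-cause pneumonia, and for IPD only if the precision rule in SAP 5.2.3 is met. At an assumed 20% share, 0.20 × 175,000 = 35,000 people. SAP Table 5.1 gives 9% to 20% for all-cause pneumonia at that size but -6% to 44% for IPD, which would fail the rule. The IPD interval excludes zero at 58,000 people but not at 43,000.

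The cost is wording in both documents and one derived variable from data already requested; SAP 5.2.2 already searches the earlier claims for PCV13. The downside is that the undetermined level may be large, especially among 2014 entrants. Claims start on January 1, 2014, so nobody first coded in the opening six months can be shown to be newly diagnosed. Report the size of that level.
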